4.5 Analysis Sets

All enrolled patients: all patients who signed the informed consent form.

Full Analysis Set (FAS): all patients who were scheduled to receive the rhPSMA-7.3 (¹⁸F) injection having met the inclusion/exclusion criteria.

Full Safety Population (FSP): all patients who received the rhPSMA-7.3 (¹⁸F) injection.

Efficacy Analysis Population (EAP): all patients who received rhPSMA-7.3 (¹⁸F) injection followed by a PET/CT scan and who underwent RP and PLND.

Extended Efficacy Population (EEP): all patients who received rhPSMA-7.3 (¹⁸F) injection followed by a PET/CT scan. This population includes M0 and M1 patients independent of performance of RP and PLND and will be used for M1 related efficacy and Kappa statistics.

Per Protocol Population (PP): All patients in the EAP population who have histology available from surgery that allows SoT determination, and without any major protocol deviations that will affect the evaluations of the PET scan or histology.

The primary analysis will be based on the EAP. The FSP will be used for all safety summaries.

Upon database release, protocol deviation and analysis set outputs will be produced and will be to BED for review. An analysis set classification meeting will be arranged to discuss the outputs and to decide which patients and/or patient data will be excluded from certain analyses. Decisions made regarding the exclusion of patients and/or patient data from the analyses, and the agreement of population inclusion for each patient, will be made prior to database lock and will be documented and approved by the Sponsor.

A by-patient listing of analysis set details will be provided. This listing will include: center, country, patient identifier, and inclusion/exclusion flag for each set and reason for exclusion from

PAREXEL International

Blue Earth Diagnostics
BED-PSMA-301

Statistical Analysis Plan

each set. All enrolled patients will appear on this listing. If patient data have been partially excluded, visit will also appear on this listing.

The number and percentage of patients in each population will be provided using all enrolled patients.

4.6 Demographic and Other Baseline Characteristics

4.6.1 Demographics

All demographics (e.g. age [including age groups of <65, \geq 65 and the subgroup of \geq 75], sex, race, height, weight and BMI at screening and on Day 1) and baseline characteristics will be listed, and their baseline characteristics summarized (with weight and BMI on day 1) using the FAS, FSP, EAP, EEP and PP.

BMI will be calculated as $BMI(kg/m^2) = \frac{weight(kg)}{height(m)^2}$

4.6.2 Baseline conventional imaging

Baseline conventional imaging will be taken from imaging performed within the 60 days before screening or will be performed prior to IP administration.

The imaging results classified as baseline (above) will be summarized using FAS, EAP, EEP and PP by imaging modality and as positive or negative for detection of N1 or M1 disease. Patients with more than one baseline scan will be summarized for the combination of baseline scans and include all applicable anatomical areas covered. A listing will contain all these baseline parameters and include the imaging modality (CT, MRI, bone Scan, etc).

4.6.3 Prostate Cancer History

Prostate cancer history will be summarized using the FAS, FSP, EAP, EEP and PP for time of initial prostate cancer diagnosis to informed consent (in months), for TNM stage, total Gleason score (Frequencies), Gleason Grade Group (GGG) based on prostate biopsy, most recent PSA including frequency by categorization (0-0.5, >0.5-1.0, >1.0-2.0, >2.0-5.0, >5.0-10.0, >10.0 [ug/L]).

This same information will be listed by patient.

Gleason Grade Group is defined by the International Society of Urological Pathologists, and the categories are as follows:

- Grade Group 1 is defined as Total Gleason score $\leqslant 6$
- Grade Group 2 is defined as Gleason score $3+4=7$
- Grade Group 3 is defined as Gleason score $4+3=7$
- Grade Group 4 is defined as Total Gleason score of 8
- Grade Group 5 is defined as Total Gleason scores 9-10

PAREXEL International

Blue Earth Diagnostics
BED-PSMA-301

Statistical Analysis Plan

TNM staging will be displayed at observed level and combined at levels T2, T3, T4, M0, M1, MX, where each of these contain underlying categories (i.e. T2 -All contains subjects with observed at T2, T2a, T2b, T2c)

4.6.4 Baseline Risk Category

Risk Category will be assigned using the NCCN Guidelines, version 1.2020; PROS-2. A listing of risk category and underlying variables will be provided. Risk category will be summarized into categories using the EAP. Risk Categories are shown in Table 1. Per the CSP, risk categories of unfavorable intermediate-risk, high-risk or very high-risk are expected.

Table 1: Risk Categories from NCCN guidelines.

Risk Group	Clinical/Pathologic Features
Very Low	T1c AND Grade Group 1 AND PSA <10 ng/mL AND Fewer than 3 prostate biopsy fragments/cores positive, $\leq 50\%$ cancer in each fragment/core AND PSA density < 0.15 ng/mL/g
Low	Has all following but does not qualify for very low risk T1-T2a AND Grade Group 1 AND PSA < 10 ng/mL
Favorable intermediate	No High or Very High-risk features 1 Intermediate Risk Factors and Grade Group 1 or 2 and $<50\%$ biopsy cores positive
Unfavorable Intermediate	No High or Very High-risk features 2 or 3 Intermediate Risk Factors. and/or Grade Group 3 and/or $\geq 50\%$ biopsy cores positive
High	No very-high risk features and has at least one high-risk feature: T3a OR Grade Group 4 or Grade Group 5 OR PSA >20 ng/mL
Very High	Has at least one of the following T3b-T4 OR Primary Gleason pattern 5 OR 2 or 3 high-risk features >4 cores with Grade Group 4 or 5

Intermediate risk factors are: T2b-T2c, PSA 10-20 ng/mL, Grade Group 2 or 3

In this study, the risk groups will be categorized into:

- “High or Very High Risk” – defined as meeting any one of these criteria: T-stage T3 (including T3a and T3b) or T4, Gleason Grade Group 4 or 5, Primary Gleason pattern 5, or PSA >20ng/mL
- “Not High or Very High Risk” – defined as not meeting any of the criteria meeting the high or very high-risk criteria.

PAREXEL International

Blue Earth Diagnostics
BED-PSMA-301

Statistical Analysis Plan

4.6.5 Medical history

Medical history will be coded using Medical Dictionary for Regulatory Activities (MedDRA) version 22.1 or higher – the data will be listed and include start date, end date, ongoing at study start, Preferred Term (PT) and System Organ Class (SOC). Medical history will also be summarized using FSP by SOC and PT.

4.7 Prior and Concomitant Medications and Procedures

Medication and/or procedure start and stop dates will be compared to the date of IP administration to allow medications/procedures to be classified as either Prior only, both Prior and Concomitant, or Concomitant only. Medications and/or procedures starting after Day 4 will be listed but will not be classified or summarized.

Medications/procedures that start and stop prior to the date of dose of IP administration will be classified as Prior only. If a medication/procedure starts before the date of IP administration and stops on or after the date of IP administration, then the medication/procedure will be classified as both Prior and Concomitant. Medications/procedures will be classified as Concomitant only if they have a start date on or after the date of first dose of study medication.

If medication/procedure start and/or stop dates are missing or partial, the dates will be compared as far as possible with the date of IP administration. Medications/procedures will be assumed to be Concomitant only, unless there is clear evidence (through comparison of partial dates) to suggest that the medication/procedure started prior to the IP administration. If there is clear evidence to suggest that the medication/procedure started prior to the IP administration, the medication/procedure will be assumed to be both Prior and Concomitant, unless there is clear evidence to suggest that the medication/procedure stopped prior to the IP administration. If there is clear evidence to suggest that the medication/procedure stopped prior to the IP administration, the medication will be assumed to be Prior only.

Medications will be coded using WHODrug Global Dictionary and summarized by ATC code (levels 2 and 4) and Preferred term and listed by patient using the FSP. In case of missing level 4 coding the level 3 coding will be used.

Procedures will be summarized by System Organ Class (SOC) and Preferred Term (PT) using MedDRA dictionary and listed by patient.

All prior and concomitant medications and procedures will be listed by patient. Concomitant medications will be summarized using the FSP.

4.8 Exposure and Treatment Compliance

A patient listing of rhPSMA-7.3 (¹⁸F) administration including total administered activity, injection site reactions, local imaging results, incidental findings, and evaluations of the independent blinded central PET readers will be provided.

PAREXEL International

Blue Earth Diagnostics
BED-PSMA-301

Statistical Analysis Plan

A summary of total administered activity will be provided using the FAS and PP. All activity will be converted to MBq using the conversion 1mCi=37 MBq.

4.9 rhPSMA-7.3 (¹⁸F) Image reading

Each rhPSMA-7.3 (¹⁸F) image will initially be read by a site-based local reader, and the results will be listed including incidental findings. In addition, for the primary endpoint analysis, imaging will be read by three blinded independent PET readers (see the study Independent Review Charter for further details). The results of the blinded PET readers will be used in the primary analysis, thus requiring each (statistical) analysis to be performed three times. In addition, the majority interpretation will be displayed.

Table 2 Derivation of Overall Interpretation (2 out of 3 readers consensus)

Reader 1	Reader 2	Reader 3	Majority
Positive	Positive	Positive	Positive
Positive	Positive	Negative	Positive
Negative	Negative	Positive	Negative
Negative	Negative	Negative	Negative

PET imaging results (i.e. positive/negative) will be summarized using the EEP by anatomical location by category and anatomical location within category. Categories will be prostate, pelvic lymph nodes, lymph nodes outside of pelvis, soft tissue/parenchyma and bones, as well as extra-pelvic (which would include lymph nodes outside of pelvis, soft tissue/parenchyma and bones together). All categories will be presented in the summary, but anatomical locations will only be presented where data are collected, i.e. lesion investigated in that anatomical location.

4.10 Biopsy/Surgery

If the rhPSMA-7.3 (¹⁸F) PET shows M1 metastatic disease, the patient will be asked to undergo a biopsy or confirmatory imaging of the PET-positive lesion(s) to confirm the presence of a metastasis. If a surgical intervention of this lesion is carried out as part of the treatment, this may substitute for a biopsy. If the patient has proven M1 metastatic disease, the disease management may be altered, based on the responsible physician's clinical judgement. This change in disease management will be documented on the eCRF.

If rhPSMA-7.3 (¹⁸F) PET does not detect M1 disease, the patient will undergo the scheduled RP and PLND. In patients without M1 lesions identified and in whom the patient and physician believe, after obtaining the results of the rhPSMA-7.3 (¹⁸F) PET, that EBRT would be a better therapeutic option than surgery, the patient may proceed to EBRT and the rationale for this change of disease management will be documented on the eCRF.

PAREXEL International

Blue Earth Diagnostics
BED-PSMA-301

Statistical Analysis Plan

The regional PLND must be performed by a suitably qualified surgeon and should include, at minimum, resection of lymphatic tissue for histological analysis from the following nodal groups: 1) hypogastric (internal iliac), 2) external iliac, and 3) obturator LNs. Extended LN dissection may be performed if clinically appropriate and the anatomical regions (e.g. presacral, common iliac, peri-rectal) with left/right designations, should be recorded on the eCRF. The location of the dissected material shall be marked in order to allow matching with their anatomical origin (left and right pelvis); the left and the right side of the specimen shall be clearly marked. The dissected LNs will be sectioned and analyzed by a pathologist for the presence or absence of PCa according to standard of care at the clinical site. The number of lymph nodes sampled and found positive for PCa will be registered and summarized.

Patients with PET M1 will be summarized using the EEP by confirmatory method(s), result of confirmation, change in disease management, surgery (radical prostatectomy and pelvic lymph node dissection) performed, Lymph node dissection and (additional) treatment received. All counts will be presented including percentage of patients categorized as PET M1.

Patients will be summarized using the EEP by surgery (RP and PLND) received, extended lymph node dissection and (additional) treatment received. All counts will be presented including the percentage of patients categorized as PET M0.

Results by patient will be listed for both M0 and M1 patients. A display of Histopathology of Pelvic Lymph Nodes and a display of confirmatory procedures will be created for all patients. For M1 patients, a listing of PSMA Positive M1 Lesions (by anatomic location), including method (Biopsy/histopathology, CT Scan, MRI, Bone scan, Other) and result, will be created.

A summary will be provided on methods to obtain standard of truth.

4.11 TNM staging and Gleason score

In addition to baseline values (Section 4.6.3), baseline and post-surgery staging will be summarized for TNM stage, primary and secondary and total Gleason score similar to baseline using the EEP. In addition, for GGG, a shift table will be presented from baseline to final staging.

4.12 Standard of Truth

Histology or confirmatory imaging will be used as the Standard of Truth (SoT), as defined below.

1. Histology
 - a. Histology of surgically removed pelvic LNs;
 - b. Histology obtained by biopsy of M1 lesion.
2. Confirmatory Imaging
 - a. In patients without available histopathology, confirmatory conventional imaging is acceptable as proof of M1 disease in case of unequivocal findings (e.g. sclerotic bone lesions on CT, positive bone lesions on bone scan, evidently enlarged LNs radiologically considered metastases, lesions in the liver representing metastases as determined by ultrasound, CT or MRI, multiple pulmonary nodules on CT).

PAREXEL International

Blue Earth Diagnostics
BED-PSMA-301

Statistical Analysis Plan

b. Confirmatory imaging for proof of M1 disease will be read centrally. Three central reviewers will review all submitted imaging and reach consensus on the nature of the target lesion. Reads of the confirmatory imaging as SoT will be directed by rhPSMA-7.3 (¹⁸F) PET findings (for confirmation of lesion location only). A brief summary of clinical information will be available to the SoT readers (e.g. 67-year-old male with newly diagnosed, localized prostate cancer prior to rhPSMA-7.3 (¹⁸F) scan). Readers will be blinded to all other information. Further details are given in the study Independent Review Charter.

3. Baseline Conventional Imaging only

a. If M1 lesion identified by blinded PET reader but not site reader, or if M1 lesion is identified by site reader but no histology or no confirmatory imaging is available, then only conventional imaging at baseline will be used to determine the SoT.

SoT will be listed next to the results of the blinded independent reads and include method (Histology/Confirmatory Imaging/Baseline Imaging only), anatomical location and Result(s) using the EEP. Histology SoT will be assessed based on local reads of the PET scan, and these results will be included irrespective of BIE reading. The SoT will be summarized by method and anatomical location.

One Positive Region; One Negative Region	PET is correct on positive region	Primary analysis: PET is negative on the positive region Secondary analysis: PET is negative on both regions only	Primary analysis: NA Secondary analysis: PET is negative on histopathology positive region and PET is positive on histopathology negative region	NA
Two Negative Regions	NA	NA	PET-positive on one or two regions	PET is negative on both regions

NA=cell classification is not applicable; PET=positron emission tomography.

Results of the Hemipelvis Categorization will be listed by region and summarized by region status using the EAP. This summary will include a category for missing Hemipelvis Categorization. The patient's by region and patient level classification will be listed including classification for the secondary analysis (Section 4.14.3.4 and 4.14.3.5).

A cross table of patients PET image diagnostic and SoT diagnostic will be provided.

PAREXEL International

Blue Earth Diagnostics
BED-PSMA-301

Statistical Analysis Plan

4.14 Efficacy Evaluation

Unless otherwise stated, all efficacy evaluations will be done using the EAP as defined in Section 4.5.

4.14.1 Analysis and Data Conventions

The primary hypothesis involves a joint assessment of sensitivity and specificity against individual performance goals:

$H_0: \text{Sensitivity} \leq Se_0 \text{ or Specificity} \leq Sp_0$ versus $H_1: \text{Sensitivity} > Se_0 \text{ and Specificity} > Sp_0$

Where Se_0 and Sp_0 are performance goals for sensitivity and specificity, respectively. Performance goals of 22.5% (Se_0) for sensitivity and 82.5% (Sp_0) were selected based on the low sensitivity but high specificity of other PSMA ligands used for lymph node staging.

The definition of Sensitivity will be:

True Positive / (True Positive + False Negative)

The definition of Specificity will be:

True Negative / (True Negative + False Positive)

Additional analysis will be performed for PPV and NPV.

The definition of PPV will be:

True Positive / (True Positive + False Positive)

The definition of NPV will be:

True Negative / (True Negative + False Negative)

The sensitivity, specificity, PPV and NPV, together with the corresponding 95% CIs, will be estimated for each of the three blinded PET readers. All analyses performed for the three blinded PET readers will be repeated for their majority evaluation (Section 4.9).

4.14.1.1 Adjustments for Covariates

Not applicable.

4.14.1.2 Handling of Dropouts or Missing Data

Missing evaluation results in the biopsy/surgery will be assigned the worst value. Hence, a side with a positive rhPSMA-7.3 (^{18}F) PET will be considered as false positive (i.e. SoT will be set to negative), while a side with negative rhPSMA-7.3 (^{18}F) PET will be a false negative (i.e. SoT set to positive).

The number and percentage of patients with missing data for the biopsy/surgery will be summarized by major reason, as indicated in Section 4.13.

Imputation of missing dates for concomitant medications and procedures is described in Section 4.7, imputation of missing dates for AEs is described in Section 4.15.1.

PAREXEL International

Blue Earth Diagnostics
BED-PSMA-301

Statistical Analysis Plan

4.14.1.3 Interim Analyses

Using the first 150 patients an interim analysis of safety data will be created. The actual outputs for this are indicated in the shells.

4.14.1.4 Examination of Subgroups

The attributes of the primary efficacy variable will be examined across subgroups based on:

- PCa risk categories (high- or very high-risk vs not high or very high risk).
- Most recent PSA values (0- 0.5, >0.5-1.0, >1.0-2.0, >2.0-5.0, >5.0-10.0, >10.0 [ng/mL])
- Race (Black or African American, American Indian or Alaska Native, Asian, Native Hawaiian or Other Pacific Islander, White, Not Reported, Other)
- Age (<65, >=65 and >=75)

The analysis within subgroups will involve the confidence intervals (CI) but not the hypothesis testing. For each of these analyses, if a category has low counts (less than 10) it may be collapsed with another category, for ordinal parameters only with neighboring categories.

A cross table of N1 disease status from rhPSMA-7.3 (¹⁸F) PET against to histopathology of pelvic LNs will be provided by risk category and associated 95% CI for Sensitivity and Specificity will be presented.

4.14.1.5 Clustered binary data estimate of variance

4.14.1.5.1 Sensitivity

Following Zhou et al. the following estimators will be used:

$$\widehat{Se} = \frac{\sum_{i=1}^I N_i * \widehat{Se}_i}{\sum_{i=1}^I N_i}$$

$$\widehat{Var}(\widehat{Se}) = \frac{1}{I(I-1)} \sum_{i=1}^I \left[\frac{N_i}{\bar{N}} (\widehat{Se}_i - \widehat{Se})^2 \right]$$

With:

Se	: Sensitivity
i	: individual patient
I	: total number of patients
N_i	: Number of elements (True Positive + False Negative) for patient i
\widehat{Se}_i	: Sensitivity for patient i
\bar{N}	: Mean cluster size

The example in Zhou et al. is coded in SAS in Appendix 6.1.

An asymptotic normal distribution for the sampling distribution of \widehat{PPV} is assumed and the 95% confidence interval will be derived as:

$$\widehat{Se} \pm Z_{1-\alpha/2} \sqrt{\widehat{Var}(\widehat{Se})}$$

where $Z_{1-\alpha/2}$ is the upper $1-\alpha/2$ value for the standard normal distribution.

PAREXEL International

Blue Earth Diagnostics
BED-PSMA-301

Statistical Analysis Plan

4.14.1.5.2 Additional Confidence interval Sensitivity

Normal approximation in constructing 95% CIs might lead to bounds exceed [0, 1] for \widehat{PPV} . Hence an additional CI will be derived. Logit transformation will be applied to PPV and Delta Method (Casella and Berger, 2021) will be utilized to obtain to approximate the variance of $\text{logit}(PPV)$. Accordingly, the asymptotical distribution of $\text{logit}(PPV)$ is

$$\sqrt{n} \left[\log \left(\frac{\widehat{Se}}{1-\widehat{Se}} \right) - \log \left(\frac{Se}{1-Se} \right) \right] \xrightarrow{d} N \left(0, \frac{1}{[Se(1-Se)]^2} \text{Var}(Se) \right).$$

Accordingly, an asymptotic normal distribution for the sampling distribution of $\text{logit}(\widehat{Se})$ is assumed and the 95% confidence interval will be derived as:

$$\text{logit}(\widehat{Se}) \pm Z_{1-\alpha/2} \sqrt{\text{Var}(\text{logit}(\widehat{Se}))}$$

where $Z_{1-\alpha/2}$ is the upper $1-\alpha/2$ value for the standard normal distribution and $\sqrt{\text{Var}(\text{logit}(\widehat{Se}))} \approx \frac{1}{[\widehat{Se}(1-\widehat{Se})]^2} \text{Var}(\widehat{Se})$. Lower and upper confidence intervals values will be reported in [0,1] scale by the logit inverse transformation, as follows

$$CI_{[0,1] \text{ scale}} = \frac{e^{CI_logit}}{1 + e^{CI_logit}}$$

4.14.1.5.3 Specificity

The formulas for sensitivity can be used with appropriate substitution.

Sensitivity=True Positive / (True Positive + False Negative)

Specificity=True Negative / (True Negative + False Positive)

4.14.2 Primary Efficacy Variable

The co-primary endpoints for the study are based on the sensitivity and specificity of rhPSMA-7.3 (^{18}F) PET (by central BIE) in detecting N1 disease compared to histopathology of pelvic LNs. The primary analysis involves a joint assessment of sensitivity and specificity against individual performance goals:

H_0 : Sensitivity $\leq Se_0$ or Specificity $\leq Sp_0$ versus H_1 : Sensitivity $> Se_0$ and Specificity $> Sp_0$

Where Se_0 and Sp_0 are performance goals for sensitivity and specificity, respectively. Performance goals of 22.5% (Se_0) for sensitivity and 82.5% (Sp_0) for specificity were selected based on the low sensitivity but high specificity of other PSMA ligands used for LN staging. The analyses for sensitivity and specificity will be performed using one-sided 0.025 exact binomial tests. In addition to the rates, exact two-sided 95% CIs will also be provided. If the predefined sensitivity and specificity goals are met by the same two of three blinded independent readers (both tests reach statistical significance [$P < 0.05$] for the same two readers), the study will be considered to have successfully demonstrated the effectiveness of the rhPSMA-7.3 (^{18}F) in detecting N1 disease.

The TP, FP, TN and FN regions will be categorized according to Table 3 (Section 4.13) using a right and left hemipelvis regional classification method. For the primary analysis, patients who have one TP region will be categorized as a TP patient.

PAREXEL International

Blue Earth Diagnostics
BED-PSMA-301

Statistical Analysis Plan

For patients who have no TP regions, Table 4 depicts the method for assigning patient level categorizations based on by-region results (i.e. for the different possible hemipelvis combinations of TN, FN and FP regions).

Classification will be summarized via a cross table of region status using the layout of Table 4b. A summary of frequency of PET Patient level Classifications will be supplied including estimates and CI of Sensitivity and Specificity according to each blinded reader. Sensitivity and Specificity will be plotted for each reader including CI and performance goals.

The primary analysis will be repeated using the PP following methods of the primary analysis: A summary of frequency of PET Patient level Classifications will be supplied including estimates and CI of Sensitivity and Specificity according to each blinded reader. Frequencies will be displayed in a bar chart. Sensitivity and Specificity will be plotted for each reader including CI and performance goals.

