16.4 Analysis of Primary Endpoint(s)

The co-primary endpoints for the study are based on the sensitivity and specificity of rhPSMA-7.3 (¹⁸F) PET (by central BIE) in detecting N1 disease compared to histopathology of pelvic LNs. The primary analysis involves a joint assessment of sensitivity and specificity against individual performance goals:

H_0 : Sensitivity $\leq Se_0$ or Specificity $\leq Sp_0$ versus H_1 : Sensitivity $> Se_0$ and Specificity $> Sp_0$

Where Se_0 and Sp_0 are performance goals for sensitivity and specificity, respectively. Performance goals of 22.5% (Se_0) for sensitivity and 82.5% (Sp_0) for specificity were selected based on the low sensitivity but high specificity of other PSMA ligands used for LN staging. The analyses for sensitivity and specificity will be performed using one-sided 0.025 exact binomial tests. In addition to the rates, exact two-sided 95% confidence intervals (CIs) will also be provided. If the predefined sensitivity and specificity goals are met by the same two of three readers (both tests reach statistical significance for the same two readers), the

study will be considered to have successfully demonstrated the effectiveness of the rhPSMA-7.3 (¹⁸F) in detecting N1 disease.

The TP, FP, TN and FN regions will be categorized according to [Table 2](#) ([Section 9.1.7](#)) using a right and left hemipelvis regional classification method. For the primary analysis, patients who have one TP region will be categorized as a TP patient.

For patients who have no TP regions, [Table 6a](#) and [Table 6b](#) depict the method for assigning patient level categorizations based on by-region results (i.e. for the different possible hemipelvis combinations of TN, FN and FP regions).

Two analyses will be performed based on the classification of patients with one TP region and one TN region. The primary analysis will include patients as FN if they only had one positive region by histopathology and it was missed by PET. Full diagnostic statistics will be provided for both patient level classifications.

Table 6: Translation of Region Level to Patient Level Categorizations in Patients with No TP Regions

a)

Patient Level Categorization	At Least one True Negative (TN) Region	At Least one False Negative (FN) Region	At Least one False Positive (FP) Region
True Negative (TN)	Yes	No	No
False Negative (FN)	Yes	Yes	No
False Negative (FN)	No	Yes	No
False Positive (FP)	Yes	No	Yes
False Positive (FP)	No	No	Yes

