4.16 Determination of Sample Size

A total sample size of approximately 375 patients is planned in order to obtain 300 evaluable patients for analysis of the primary endpoint. Assuming a sensitivity of 40% of PSMA ligands for detecting N1 disease (based on the previous OSPREY [NCT02981368]), a sample size of 75 positive cases provides 90% power to reject the performance goal of 22.5%. Assuming a specificity of 90% for rhPSMA-7.3 (¹⁸F) PET, a sample size of 225 negative cases provides 90% power to reject the performance goal of 82.5%. Assuming the true prevalence rate of N1 disease is 25%, a sample size of 300 evaluable patients is expected to provide 75 positive cases and 225 negative cases.

Up to approximately 375 patients with unfavorable intermediate-, high- and very high-risk PCa will be enrolled into the study. Since some patients will have M1 disease and some patients will receive EBRT instead of RP following the PET scan, enrollment of up to approximately 375 patients will ensure inclusion of at least 300 evaluable patients undergoing RP and PLND.

In order to have sufficient numbers of histologically positive and negative cases, an interim look will be allowed to ensure a distribution of pN1 disease as would be anticipated in this patient population. After the inclusion of approximately 150 patients, the percentages of pN0 and pN1 will be monitored. If the percentage of pN1 exceeds 35%, inclusion of very high-risk and/or high-risk patients will be suspended. If the percentage of pN1 is less than 15%, the inclusion of intermediate-risk patients will be suspended.

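### The SAP's success rule uses P < 0.05 although the co-primary tests are one-sided at 0.025, doubling the nominal error rate of each test

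*SAP*

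**What the plan says.** SAP 4.14.2 states that the co-primary analyses are "performed using one-sided 0.025 exact binomial tests", against goals fixed as follows: "Performance goals of 22.5% (Se_0) for sensitivity and 82.5% (Sp_0) for specificity were selected". The alternative hypothesis is one-sided for both measures (greater than the goal). On intervals the section says: "In addition to the rates, exact two-sided 95% CIs will also be provided". It then defines success as both goals being met by the same two of the three blinded readers, explained in brackets as "both tests reach statistical significance [$P < 0.05$] for the same two readers".

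Protocol 16.4 specifies the same tests: "The analyses for sensitivity and specificity will be performed using one-sided 0.025 exact binomial tests". Its success sentence follows the same two-reader rule but ends at "both tests reach statistical significance for the same two readers", with no P threshold. The bracket therefore first appears in the SAP. SAP 4.17, which lists changes to the planned analysis, does not mention it. The SAP introduction says the SAP prevails where the two documents differ.

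**The concern.** A P-value from a one-sided test at level 0.025 has to be compared with 0.025. The SAP compares it with 0.05, in the one sentence that decides whether the trial has demonstrated effectiveness. A programmer who sets the P-value from the specified test against the printed threshold would be following the SAP and would be testing at twice the stated level.

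The rule would also come apart from the intervals. An exact two-sided 95% interval leaves 2.5% in each tail, so its lower limit corresponds to a one-sided test at 0.025. Under P < 0.05 a reader could meet a goal while that reader's reported interval still contains it. SAP 4.14.2 calls for a plot of each reader's estimate with its interval and the performance goals, so the contradiction would appear in the trial's own figure.

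**Working it through.** **Inputs.** Goals 22.5% and 82.5% (SAP 4.14.2). From SAP 4.16: 75 positive and 225 negative cases, assumed sensitivity 40%, assumed specificity 90%, and 90% power for each test. Level: one-sided 0.025 (SAP 4.14.2, Protocol 16.4).

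**Formulas.** For n cases, goal p0 and assumed value p1, the cut-off r is the smallest count with P(X ≥ r | n, p0) ≤ α. The exact size is that tail probability, and the power is P(X ≥ r | n, p1). Intervals are Clopper-Pearson.

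**Step 1: reproduce the stated power.** For sensitivity the SAP says "a sample size of 75 positive cases provides 90% power to reject the performance goal of 22.5" percent. The same calculation applies to specificity.

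| Test | One-sided level | Cut-off | Exact size | Power |
|---|---|---|---|---|
| Sensitivity, n = 75 | 0.025 | 25 (33.3%) | 0.0207 | 0.904 |
| Sensitivity, n = 75 | 0.05 | 24 (32.0%) | 0.0373 | 0.939 |
| Specificity, n = 225 | 0.025 | 197 (87.6%) | 0.0246 | 0.906 |
| Specificity, n = 225 | 0.05 | 196 (87.1%) | 0.0378 | 0.936 |

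The stated 90% is recovered at 0.025 and not at 0.05, so the sample size was built on 0.025.

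**Step 2: effect on error.** The nominal level per test goes from 0.025 to 0.05, a factor of 2. Because the binomial is discrete, the attained size rises by less:

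- Sensitivity: 0.0373 / 0.0207 = 1.80.
- Specificity: 0.0378 / 0.0246 = 1.54.

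**Step 3: compare with the planned intervals.**

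| Result | One-sided P | P < 0.05? | P < 0.025? | Exact 95% CI | Contains the goal? |
|---|---|---|---|---|---|
| 24/75 | 0.0373 | yes | no | 21.7% to 43.8% | yes (22.5%) |
| 25/75 | 0.0207 | yes | yes | lower limit 22.9% | no |
| 196/225 | 0.0378 | yes | no | 82.0% to 91.2% | yes (82.5%) |
| 197/225 | 0.0246 | yes | yes | lower limit 82.52% | no |

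The 0.025 rule agrees with the interval in every row. The 0.05 rule disagrees with it at 24/75 and at 196/225.

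**Step 4: try the bracket as a two-sided P.** Doubling the one-sided tail gives:

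- 24/75: 2 × 0.0373 = 0.0745, fails.
- 25/75: 2 × 0.0207 = 0.0415, passes.
- 196/225: 2 × 0.0378 = 0.0756, fails.
- 197/225: 2 × 0.0246 = 0.0492, passes.

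These are the 0.025 cut-offs again. However, the exact two-sided P that sums point probabilities is 0.0529 at 197/225, which fails; it first passes at 198/225 (0.0282). The bracket thus allows three specificity cut-offs, 196, 197 or 198, depending on which P is meant.

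**The case against.** The strongest reply is that the bracket means a two-sided P. The SAP does not say which P it refers to, and the same paragraph plans two-sided 95% intervals. If P is the doubled tail, P < 0.05 is the same rule as one-sided 0.025. There is then no inflation and no conflict with the interval, only loose wording. The rest of the plan supports 0.025 as the intention: the level is stated outright, the power depends on it, and no change of alpha is listed in SAP 4.17.

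This is a fair account of what the authors probably meant, but it does not rescue the sentence. The SAP describes no two-sided test for the co-primary endpoints, and Step 4 shows that the two-sided reading is not unique.

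Three further points stand as limits on the size of the problem:

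- The doubling concerns the nominal level. Attained size rises 1.80-fold and 1.54-fold.
- At the planned numbers the two levels differ at only one count per test. Under the design assumptions a given reader lands on exactly 24/75 with probability about 3.5%, and on exactly 196/225 with about 3.0%.
- Such a count meets one goal for one reader. Trial success needs both goals met by the same two readers.

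It is also true that the SAP's precedence clause does not settle the matter. On the test level the two documents agree, and the conflict lies between two sentences of the SAP. The clause does mean that the protocol's clean wording cannot be relied on to override the bracket.

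**Conclusion.** The concern holds. SAP 4.14.2 contradicts itself within one paragraph on the significance level of the trial's success criterion. Taken with the only tests the SAP describes, the bracket doubles the nominal level of each co-primary test and lowers each cut-off by one patient at 75 positive and 225 negative cases. The two borderline counts it admits have exact 95% intervals that contain the goals.

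The cut-offs and sizes rest on the planned case numbers and will shift if the realised numbers differ; the twofold ratio of nominal levels will not. The result is per test and per reader. No trial-level error rate under the two-of-three-reader rule has been computed. The effect is small in patients, but it must be corrected because a borderline result would otherwise lead to an argument, after the data are known, about which level applied.

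**What to change.** In SAP 4.14.2, replace the bracketed threshold with: one-sided P < 0.025, equivalently the lower limit of the exact two-sided 95% confidence interval exceeds the performance goal. Writing ≤ in place of < gives the same cut-offs at the planned case numbers. Deleting the bracket, so that the sentence matches Protocol 16.4, would also remove the contradiction, but naming the level and tying it to the interval leaves less to interpret.

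The cost is one edit in the SAP. Sample size, power, data collection and conduct are unchanged. Compared with the literal P < 0.05 rule, the criterion becomes stricter by one patient per test; compared with the stated 0.025 level, nothing changes.
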